## **6.6 Study Drug Accountability**

The Investigator has the ultimate responsibility for the study drug accountability at the study site. The Investigator or a designated individual (eg, pharmacist or another appropriate person) will maintain records of the study drug's delivery to the study site and to the subject, the inventory at the site (used and unused product containers), the use by each subject, and the return to the sponsor or alternative disposition of unused medication. The study drug must be kept in a locked area that is monitored for temperature at least once per day. Access to study drug will be restricted to authorized study personnel and used only in accordance with the approved protocol. At the conclusion of the study, any remaining study drug supplies will be returned to the sponsor or its designee. The sponsor or its designee will ensure that a final report of study drug accountability is prepared and maintained by the Investigator. The Investigator agrees not to supply or administer study drug to any person except those subjects participating in this study.

## **6.7 Assessment of Subject Compliance**

Compliance will be based on the amount of study drug dispensed to the subject and returned to the site.

# **7. STUDY PROCEDURES AND ASSESSMENTS**

Under Amendment 7 and subsequent amendments, subjects with open epiphyseal growth plates will undergo knee and hand/wrist radiographs (AP view) at the clinical site every 6 months. Additional knee and hand/wrist radiograph assessments will also be performed every 3 months ( $\pm 2$  weeks) in skeletally immature subjects who (1) received flare up dosing in the period of time since their last assessment; and (2) had not achieved 100% skeletal maturity on their last assessment. These radiographic assessments will not be performed remotely unless the Investigator determines they can be performed at a local medical facility. A description of the knee and hand/wrist radiograph assessments is provided in Section 7.3.2.

## **7.1 Screening, Recruitment, and Informed Consent**

Once the PVO-1A-202 Protocol Amendment 8 is approved at the clinical site, subjects currently enrolled in the study will be contacted, informed about the Amendment 8 changes, and given the opportunity to enroll under this amendment.

Subjects who began non-flare-up-based treatment during Part B will continue the same visit schedule into Part C, and will receive non-flare-up-based treatment for up to an additional 48 months. Subjects who started non-flare-up-based treatment during Part C will receive non-flare-up-based treatment for up to 48 months.

Part D was added for skeletally immature subjects who stopped taking study drug for any reason before completion of Part A/B/C. Part D includes yearly visits for up to a 2-year follow-up period following last dose. Maximum length of study is 72 months. No dosing will occur during Part D.

Due to the burden of travel, subjects may undergo an Institutional Review Board (IRB)-approved remote consent/assent process that will include a discussion with the site representative of the study requirements and risks. Signed consents will be emailed or faxed between site and subjects. Potential subjects/parents wishing to participate must sign the informed consent/assent per local requirements prior to undergoing any study-related procedures. Remote consent/assent will allow the screening process to begin prior to the initial site visit, should the Investigator deem it relevant.

As per the global addendum (dated 15Apr2020) to Study PVO-1A-202 Amendment 7, Investigators, in consultation with their site IRB/IEC, are required to inform subjects of the temporary changes (during the COVID-19 global pandemic) to the study conduct and monitoring plans that could impact them and their willingness to continue participation in the trial. The method of communication to subjects (e.g., email, phone call, information letter) and documentation of subject/caregiver acknowledgement is to be performed and documented in accordance with local regulations/EC requests and guidance. All contacts with subjects must be filed in the source records.

## **7.2 Safety Assessments**

Subjects will follow all procedures and undergo all assessments as outlined in the Schedule of Assessments in [Table 1](#), [Table 2](#), [Table 3](#), and [Table 4](#), as appropriate, unless a subject is unable to undergo a procedure due to safety concerns (eg, risk of flare-up) or physical limitation (pain or locked position).

### **7.2.1 Medical History and Flare-Up Assessment**

There will be no new subjects in Part C and a repeat medical history is not necessary.

For subjects receiving flare-up-based treatment, the flare-up assessment will include subject-reported current flare-up location, symptoms, and probable causes, documented on Flare-up Day 1. This will be recorded for each flare-up and intercurrent flare-up within a cycle.

### **7.2.2 Physical Examination**

For subjects from Part B continuing non-flare-up-based treatment into Part C, a physical examination of all body systems is to be documented at Months 12, 24, 36, 48, 60, and 72.

For subjects from Part B starting non-flare-up-based treatment during Part C, a physical examination of all body systems is to be documented at Part C Screening and at Months 6, 12, 24, 36, and 48.

For subjects in Part D, a physical examination of all body systems is to be documented at Year 1 and Year 2 post last dose of study treatment.

The physical examination will monitor for objective changes and for possible adverse reactions associated with therapy. Any post-baseline abnormal physical examination findings assessed as clinically significant will be recorded as AEs.

### **7.2.3 Body Weight and Linear Growth Assessments**

For subjects from Part B continuing non-flare-up-based treatment into Part C, body weight will be documented every 3 months (Months 3, 6, 9, 12, 15, 18, 21, 24, 27, 30, 33, 36, 39, 42, 45, 48, 51, 54, 57, 60, 63, 66, 69 and 72).

For subjects from Part B starting non-flare-up-based treatment during Part C, body weight will be documented at Part C Screening and every 3 months (Months 3, 6, 9, 12, 15, 18, 21, 24, 27, 30, 33, 36, 39, 42, 45 and 48).

For subjects receiving flare-up-based treatment, body weight will be recorded at Flare-up Cycle Safety Day 1 and every 12 weeks thereafter during safety assessments until treatment of the last flare-up or traumatic event in the flare-up cycle is completed.

Subjects from Part B continuing non-flare-up-based treatment into Part C with open epiphyseal growth plates at the most recent assessment will have linear growth assessments (in triplicate) by stadiometer and knee height measurements (in triplicate) at Months 6, 12, 18, 24, 30, 36, 42, 48, 54, 60, 66 and 72.

Subjects from Part B starting non-flare-up-based treatment during Part C that are under the age of 18 years and who enrolled with open epiphyseal growth plates at the most recent assessment will have linear growth assessments (in triplicate) by stadiometer and knee height measurements (in triplicate) at Screening. Subjects with open epiphyseal growth plates will also be evaluated at Months 6, 12, 18, 24, 30, 36, 42, and 48.

For subjects in Part D, body weight will be documented at Year 1 and Year 2 post last dose of study treatment. Subjects in Part D will have linear growth assessments (in triplicate) by stadiometer and knee height measurements (in triplicate) at Year 1 and Year 2 post last dose of study treatment.

Once a subject is 18 years old, triplicate linear growth and knee height assessments will no longer be required. In Part D subjects will stop participation once they reach 18 years of age.

Linear growth measurements will be performed by trained and qualified study personnel. The stadiometric measurement instructions will include practices that reduce measurement error including calibration of equipment, proper subject positioning, and measurement capture. The same examiner should be used whenever possible to standardize the performance of procedures and minimize the inter-examiner variability. Measurement of knee height will also be standardized.

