Study Design	
A Phase 2, multicenter, open-label study that will explore different dosing regimens of palovarotene in adult and pediatric subjects with FOP.
 
Part A includes all data obtained prior to Amendment 3 (dated 10 March 2016) during which pediatric and adult subjects successfully completing Study PVO-1A-201 were enrolled and followed for up to 36 months. Any subject experiencing an eligible flare-up under Part A received treatment with open-label palovarotene at a dose of 10 mg once daily for 14 days followed by 5 mg once daily for 28 days (or weight-based equivalent) and underwent all study procedures as specified in the original protocol, Amendment 1, and Amendment 2.
 
Part B includes all data obtained under Amendment 3 (dated 10 March 2016) during which subjects successfully completing Study PVO-1A-201 (including any subject who participated in Part A of Study PVO-1A-202) as well as up to 20 new adult subjects were followed for up to 24 months.
 
Part C includes all data obtained under Amendment 4 (dated 01 September 2017) and subsequent amendments during which subjects who participated in Part B will be followed for up to an additional 48 months. There will be no new subjects in Part C. Part C plus Part D total duration will not exceed 48 months.
 
Part D annual post last dose of study treatment assessments for up to 2 years will be obtained in subjects who were skeletally immature at the time of study treatment discontinuation in order to obtain longer-term safety data. No new subjects will be enrolled into Part D. Subjects will follow assessments as outlined in Table 4 for as long as they are not 100% skeletally mature. Part C plus Part D total duration will not exceed 48 months.
 
Non-Flare-up-based Treatment

---

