**Table 4. Schedule of Assessments for Part D**

Assessment/Procedure	Y1 and Y2 Post Treatment Site Visit 
Informed consent 	X
Knee and hand/wrist radiographs 	X
Linear and knee height growth assessments (<18 years of age) 	X
Physical examination	X
Body weight 	X
Vital signs 	X
Low-dose, WBCT scan (excluding head)	X
Prior/concomitant medications 	At every subject contact
Adverse events 	At every subject contact

 Year 1 (Y1) and Year 2 (Y2) visits following the last dose of study drug will be done within the total study duration from enrolment from Part A. Y1 to be completed in the window of  $\geq 6$  to  $< 18$  months post last dose of study drug. If Part A, B or C EOS date is within the Y1 window then the EOS will serve as the Y1 visit. If Part A, B or C EOS date is prior to Y1 window then Y1 should be scheduled  $\geq 6$  months from Part A, B or C EOS date but still within the Y1 window. Y2 to be completed  $\geq 18 - 24$  months post last dose of study drug. If Part A, B or C EOS date is within the Y2 window then the EOS will serve as the Y2 visit. If Part A, B or C EOS date or Y1 date (if applicable) is prior to Y2 window then Y2 should be scheduled  $\geq 6$  months from the Part A, B or C EOS date or the Y1 date, whichever is later, but still within the Y2 window. If subjects had their last dose of study medication and completed Part A, B or C EOS more than 2 years prior to their consent for Part D, then these subjects will only complete Y2 following their consent for Part D.

 Assessments may be performed remotely (eg, at the subject’s home by qualified study personnel, at a local medical facility, or via videoconference or telephone contact from clinical site personnel) unless the Investigator deems that a site visit is necessary.

 Part D informed consent is required prior to conducting Part D assessments/procedures.

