 Subjects found to be skeletally immature will continue knee and hand/wrist radiographs, and linear and knee height measurements (all in triplicate) at Year 1 (Y1) and Year 2 (Y2). Limb/joint AEs in these subjects will be evaluated by any clinical and radiographic assessments deemed appropriate by the Investigator. Once a subject has achieved 100% skeletal maturity (confirmed by radiography and defined by growth plate closures), knee and hand/wrist radiographs will no longer be required, and this will serve as their Part D study completion. In addition, once a subject is 18 years old, linear and knee height growth assessments will no longer be required. If 100% skeletal maturity is not achieved at both locations, then only the location that is still maturing would need to be monitored.

 Knee and hand/wrist radiograph assessments will be conducted at the clinical site unless the Investigator determines they can be performed at a local medical facility. All assessments will be performed at the clinical site if the radiographs cannot be performed locally.

 At each AE assessment, the Investigator must ask the subject about any joint-related complaints.

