### 3. STUDY DESIGN

#### 3.1 Overview of the Study Design

This is a Phase 2, multicenter, open-label extension study that will explore different dosing regimens of palovarotene in adult and pediatric subjects with FOP.

**Part A** includes all data obtained prior to Amendment 3 (dated 10 March 2016) during which pediatric and adult subjects successfully completing Study PVO-1A-201 were enrolled and followed for up to 36 months. Any subject experiencing an eligible flare-up under Part A received treatment with open-label palovarotene at a dose of 10 mg once daily for 14 days followed by 5 mg once daily for 28 days (or weight-based equivalent) and underwent all study procedures as specified in the original protocol, Amendment 1, and Amendment 2.

**Part B** includes all data obtained under Amendment 3 (dated 10 March 2016) during which subjects successfully completing Study PVO-1A-201 (including any subject who previously participated in Part A of Study PVO-1A-202) as well as up to 20 new adult subjects were followed for up to 24 months.

**Part C** includes all data obtained under Amendment 4 (dated 01 September 2017) and subsequent amendments during which subjects who participated in Part B will be followed for up to an additional 48 months. There will be no new subjects in Part C. Part C plus Part D total duration will not exceed 48 months.

**Part D** annual post last dose of study treatment assessments for up to 2 years will be obtained in subjects who were skeletally immature at the time of study treatment discontinuation in order to obtain longer-term safety data. No new subjects will be enrolled into Part D. Subjects will follow assessments as outlined in [Table 4](#) for as long as they are not 100% skeletally mature. Part C plus Part D total duration will not exceed 48 months.

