  - 4 Subjects found to be skeletally immature will continue knee and hand/wrist radiographs, and linear and knee height measurements (all in triplicate) at Year 1 (Y1) and Year 2 (Y2). Limb/joint AEs in these subjects will be evaluated by any clinical and radiographic assessments deemed appropriate by the Investigator. Once a subject has achieved 100% skeletal maturity (confirmed by radiography and defined by growth plate closures), knee and hand/wrist radiographs will no longer be required, and this will serve as their Part D study completion. In addition, once a subject is 18 years old, linear and knee height growth assessments will no longer be required. If 100% skeletal maturity is not achieved at both locations, then only the location that is still maturing would need to be monitored.
  - 5 Knee and hand/wrist radiograph assessments will be conducted at the clinical site unless the Investigator determines they can be performed at a local medical facility. All assessments will be performed at the clinical site if the radiographs cannot be performed locally.
  - 6 At each AE assessment, the Investigator must ask the subject about any joint-related complaints.
- Note: References to Parts B/C/D are to PVO-1A-202 Parts B/C/D which corresponds to PVO-1A-204, ongoing in France.  
 AE = adverse event; WBCT = whole-body computed tomography; Y = year;

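### Section 7.2.3 ends Part D at age 18, while the rest of the protocol ends it at growth-plate closure and at 18 drops only the height measurements

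*Protocol*

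**What the plan says.** Two rules for leaving Part D stand in the current text.

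**Age rule.** Section 7.2.3 of PVO-1A-202, repeated in Section 7.2.3 of PVO-1A-204: "In Part D subjects will stop participation once they reach 18 years of age". The sentence just before it says only that the triplicate height and knee-height measurements are dropped at 18.

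**Maturity rule.**
- The PVO-1A-202 synopsis and Section 3.1 apply Table 4 "for as long as they are not 100% skeletally mature". The synopsis of each protocol also says that Part D participation ends at skeletal maturity.
- Table 4 footnote 4, in both protocols, says of radiographically confirmed closure "and this will serve as their Part D study completion". On age it says only that "once a subject is 18 years old, linear and knee height growth assessments will no longer be required".
- In the Table 4 grid the age limit sits on the row "Linear and knee height growth assessments (<18 years of age" and not on the radiograph row.
- Section 7.3.2, in both protocols, schedules Part D radiographs at Y1 and Y2 and stops radiographs when all assessed plates have closed. It gives no age limit.

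Follow-up is bounded in any case: at most Y1 and Y2, up to 2 years after last dose, and "Part C plus Part D total duration will not exceed 48 months".

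**The concern.** Section 3.2 explains that Part D was added on the data monitoring committee's recommendation because premature growth-plate closure had been identified as a serious risk. Its stated objective is to continue safety assessment for up to 2 years after last dose in skeletally immature subjects.

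A site that follows Section 7.2.3 discharges a subject who turns 18 with an open plate. A site that follows Table 4 brings the same subject back for the remaining visit. Discharge ends the knee and hand/wrist radiographs, examination, whole-body CT and adverse-event collection. In PVO-1A-202 it also brings forward the end of serious adverse event reporting, which Section 9.1.10 runs to 30 days after study completion including Part D.

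The growth-plate information lost is radiographic, because Section 7.3.3 already limits CT growth-plate reads to subjects under 18. Follow-up on the main safety question would then differ by site according to which section was read.

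**Working it through.** **Can the rules be read together?** Take a subject in Part D who turns 18 before Y1 or Y2 with one plate still open.

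| Source | What happens at 18 |
|---|---|
| Section 7.2.3 | Participation ends; no further visit |
| Section 3.1 (PVO-1A-202) | Table 4 continues, because the subject is not fully mature |
| Table 4 footnote 4 | Height and knee height stop; radiographs continue; Part D is complete only at closure |
| Section 7.3.2 | Y1 and Y2 radiographs continue until the plates close |

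Reading the rules as whichever comes first does not work. Table 4 governs Part D only, so its provision for 18-year-olds and its age limit on the height row would have nothing to act on if nobody aged 18 could be in Part D. Footnote 6 of Tables 1 and 2 makes the same split in the treatment phase: radiographs until maturity, heights until 18. Section 7.2.3 is the outlier.

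**Who loses what under Section 7.2.3.** The inputs are the windows in Table 4 footnote 1: Y1 from 6 to under 18 months after last dose (12 months wide) and Y2 from 18 to 24 months (6 months wide). Let *a* be age in years at last dose. The subject turns 18 at (18 − *a*) × 12 months after last dose.

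- Already 18 when Y1 opens: *a* ≥ 18 − 6/12 = 17.5. Y1 and Y2 are both lost.
- Already 18 when Y2 opens: *a* ≥ 18 − 18/12 = 16.5. Y2 is lost.
- For *a* between 16.5 and 17.5, the Y1 window left is (18 − *a*) × 12 − 6 months. At 16.5 this is 18 − 6 = 12 of 12, so Y1 is intact. At 17.0 it is 12 − 6 = 6 of 12.
- Turns 18 inside the Y2 window: *a* from 18 − 24/12 = 16.0 to under 16.5. Only the Y2 window is shortened.

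An exception applies to all of these: "If Part A, B or C EOS date is within the Y1 window then the EOS will serve as the Y1 visit". Footnote 1 has the same provision for Y2, so a subject whose end-of-study visit already counts does not lose that visit.

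**Late entrants.** For subjects whose last dose and end-of-study visit were both more than 2 years before Part D consent, "then these subjects will only complete Y2 following their consent for Part D". Age at consent then decides. With a gap of *g* years from last dose to consent, the cut-off age at last dose is 18 − *g*: 15.0 for *g* = 3 and 14.0 for *g* = 4. These gaps are illustrative; the protocol does not say that such subjects exist.

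**Subjects stopped by the clinical hold.** A subject under 14 on 04 December 2019 turns 18 only after 04 December 2023. With a last dose at the hold, 24 months ends in December 2021, when the subject is under 16. This group is not affected.

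**The case against.** The best defence is that the age rule may be intended. It is unqualified and appears identically in two protocols finalised on different dates. Section 3.1, when it sets weight-adjusted dosing, describes skeletally immature subjects as under 18 with less than 90% maturity. The synopsis safety summary describes radiographs in under-18s with open epiphyses, and the CT growth-plate reads stop at 18. The age-18 clause in Table 4 could be wording carried over from Tables 1 and 2.

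These points make an age limit conceivable, but they do not reconcile the text. The Section 3.1 description is a dosing definition applied at Screening, and the safety summary sets no Part D exit. Even if footnote 4 was carried over, Section 3.1 and Section 7.3.2 still set the end by maturity. The documents do not prove which rule was meant, but most of the Part D text and its stated objective favour maturity.

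The objection about consequence has more weight. Section 7.7 regards subjects aged 14 and over as at or near adult height and allows radiographs at 90% maturity or above to be postponed. Section 1.1.3.2 expects the greater growth impact in the youngest subjects. This limits the size of the problem but does not remove the conflicting instructions.

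Keeping 18-year-olds in Part D would call for adult consent. That is routine, and treated subjects already pass 18 under Tables 1 and 2.

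**Conclusion.** The contradiction is real, is in the current text of both protocols, and should be corrected. It affects only subjects who turn 18 with an open growth plate before completing Y2. For those seen within the Table 4 windows this means roughly age 16 or over at last dose: both visits lost from 17.5, Y2 lost from 16.5, and a shortened Y2 window between 16.0 and 16.5. Late entrants could be affected from a younger age at last dose.

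The boundaries assume that no end-of-study visit already stands in for Y1 or Y2. The number of subjects is not given and is probably small. The primary efficacy analysis is unaffected. What is at stake is uniform and complete off-treatment growth-plate follow-up, which is the purpose of Part D.

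**What to change.** In Section 7.2.3 of PVO-1A-202 and of PVO-1A-204, delete the sentence that ends Part D at 18, or reword it so that only linear and knee height measurements stop at that age. Part D then ends at the earliest of 100% skeletal maturity at the knee and hand/wrist, completion of Y2, or the existing 48-month limit on Part C plus Part D.

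The cost is one sentence in each protocol, plus adult consent for any subject who turns 18 during follow-up. No procedure is added beyond Table 4. The 48-month limit, the under-18 limit on CT growth-plate reads and the planned analyses stay as they are. If the sponsor does intend an age-18 exit, Section 3.1, Section 7.3.2 and Table 4 must be changed to say so, with a reason for stopping radiographs in subjects whose plates are still open.
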